2.2.2 Secondary Endpoints

- 1) Post-concussion symptom burden measured using the Rivermead post-concussion questionnaire
- 2) Mood measured using the PHQ9 questionnaire
- 3) Quality of sleep measured using the Pittsburgh Sleep Quality Index
- 4) Functional status measured by Glasgow Outcome Score Extended
- 5) Healthcare utility questionnaire
- 6) Time to return to work
- 7) Willingness to be randomised in future randomised trials
- 8) Patient recruitment rates

3 STUDY DESIGN

The HeadOn feasibility study is a prospective feasibility study of patients presenting to the Edinburgh Royal Infirmary and St John's Hospital Emergency Departments (ED) (**Figure 1**). Patients will be identified from the ED. Potentially eligible patients will be contacted by a member of the Emergency Medicine Research Group Edinburgh (EMERGE) research team and their consent will be sought for participation. Those not recruited at presentation to the ED will be contacted by telephone, text or email within two weeks of their concussion date to seek their participation in the study, again by a member of the EMERGE research team. After consenting, the participant will be taken through the registration process for the HeadOn program. For patients who are contacted after discharge they will be taken through registration process over the telephone or if preferable will be able to return to the ED to go over the process.

At registration the participant will be invited to complete a series of patient reported measures including the Rivermead post-concussion questionnaire, Pittsburgh Sleep Quality Index, PHQ9 questionnaire and FAST alcohol questionnaire within the HeadOn program. Alongside this, a series of researcher-led anonymised data points will be collected in a separate specially designed database including demographics, date of concussion, neurological and imaging findings which will all be collected from the medical notes and imaging reports. The HeadOn program runs for five weeks following which the participant will be invited to complete the same set of outcome measures. Alongside this, all the participant will be contacted (via telephone, text or email) by a member of the research team at week 5 to complete a further five measurements: Glasgow Outcome Score Extended, mHealth App Usability questionnaire, time to return to work and a healthcare utility questionnaire. Interested participants will be invited back within two months of enrolling in the study for a more detailed qualitative interviews about HeadOn. The study will recruit for a period of 6-months or up to 100 participants.

[figure not shown]

Figure 1: Schematic of HeadOn study design

4 STUDY POPULATION

4.1 NUMBER OF PARTICIPANTS

The study aims to recruit over a 6-month period at the Royal Infirmary of Edinburgh and St John's Hospital ED with the aim to recruit 100 participants.

4.2 INCLUSION CRITERIA

- Patients aged 16 years and older (no upper age limit)
- Presenting to the ED with a concussion
- Concussion defined as a traumatically induced alteration of mental status (either defined as loss of consciousness and/or amnesia)
- Patient is Glasgow Coma Scale score of 13-15 on initial presentation to the ED
- Patient needs to be able to start using HeadOn within 14 days of their head injury

4.3 EXCLUSION CRITERIA

- Patients aged under 16 years old
- Patients requiring surgical management of their cranial injury
- Significant other associated injuries requiring hospitalisation (spinal injury, fractures, abdominal, cardiothoracic or vascular injuries)
- Does not have capacity to give consent
- Non-English speakers
- Patient in police custody or in prison

4.4 CO-ENROLMENT

Co-enrolment will be permitted with any other study provided it is not expected to place an undue burden upon participants and their families, and will not compromise the primary endpoint of either trial. Co-enrolment will only be permitted with agreement of the Chief Investigators of both studies. A written co-enrolment agreement will not be sought for co-enrolment with this study.

5. PARTICIPANT SELECTION AND ENROLMENT

5.1 IDENTIFYING PARTICIPANTS

Patients will be identified in the ED. The EMERGE team, where it is locally agreed that they are part of the clinical care team, will identify patients using triage information and clinical or electronic records in the ED at presentation or through screening of admission logs. In this case, it is anticipated they would identify patients and make the first approach. Any member of the clinical team who has received general and trial specific training and is on the delegation log may also identify patients in this way.

Patients with concussion do not typically have long stays in ED and can be discharged after a few hours. Those patients that are not approached at admission or not recruited at presentation to the ED will be identified through ED admission logs by a member of the EMERGE team and will be contacted within two weeks from the date of their concussion to seek their participation in the study by a suitably trained member of the research team.

5.2 CONSENTING PARTICIPANTS

Potentially eligible patients within the ED will be screened by the EMERGE team and approached and verbal consent gained on whether they would be interested to participate by a suitably trained member of the research team. Following this, the patient will be provided with a participant information leaflet (paper or digital). Potential participants will be recruited to the study within the four hour management window in ED. If the patient requires more time to decide

they can express an interest to participate after discharge from ED up to 14 days from the date of their concussion. Those interested to take part in the study will be consented by a member of the research team using the RedCap e-consent function which will be linked through the HeadOn website (www.headon-health.com/research).

Patients that are discharged before they agree to participate in the study or are identified post-discharge can be enrolled in the study by a suitably trained member of the research team up to 14 days from the date of their concussion. Initially patients will be contacted to see if they are interested in receiving information about the study. Those that are will be directed to the HeadOn website or sent the material by their preferred means (email/post). If they are interested in participating, the patients will be directed to the HeadOn website to be consented using the RedCap e-consent function.

5.2.1 Withdrawal of Study Participants

Participants are free to withdraw from the study at any point or a participant can be withdrawn by the Investigator. If withdrawal occurs, the primary reason for withdrawal will be documented in the participant's case report form, if possible. The participant will have the option of withdrawal from all aspects of the study but continued use of data collected up to that point. To safeguard rights, the minimum personally identifiable information possible will be collected.

6. DATA COLLECTION

Data will be collected at four points during the study period: at baseline, during the HeadOn program, at the final 5-week follow-up and during a voluntary qualitative interview. Two forms of data will be collected: patient-reported and researcher collected.

At baseline, participants will complete four patient questionnaires within the HeadOn program (Rivermead postconcussion, PHQ9, Pittsburgh Sleep Quality and the FAST alcohol screen). Researchers will also capture demographic, clinical and imaging findings data taken from participants notes and investigation finding reports. During the HeadOn program, participants will undergo a series of ecological momentary assessments (EMAs) aimed at capturing information about their symptoms, mood, thoughts about their concussion and behaviour (**Appendix**). This includes a symptom and mood diary which will be delivered daily. Alongside this, a series of other EMAs are delivered to the participant at different stages of the program (**Figure 2**): Stage 3 (Alcohol tracker), Stage 4 (Thought diary) and Stage 5 (Goal setting). HeadOn generates automated reminders (by email or notification) to help keep participants engaged. In the final 5-week follow-up of the study, both participant-reported and researcher collected outcome measures will be captured. Participants will complete the following questionnaires digitally through the HeadOn program: Rivermead postconcussion, PHQ9, Pittsburgh Sleep Quality and FAST alcohol screen. The participant will also be contacted by a trained member of the HeadOn research team to complete four questionnaires: the mHealth app usability questionnaire, healthcare utility, return to work questionnaire and the Glasgow Outcome Score Extended (GOSE). The participant will also be reminded to complete the week 5 patient-reported questionnaires if they had not already done so. If the participant has not completed these questionnaires by week 6, then they will be contacted again by a member of the research team to complete these questionnaires.

Patients who have consented to take part in qualitative interviews will be contacted (by phone or email) and invited to participate in an in-depth interview with a member of the research team. Any participant who declines to be interviewed will also be offered to provide their feedback in an online survey. Interviews will be conducted over the telephone or videoconference and will last approximately 40-60 minutes (**Appendix**). Participants will be asked for their views and experiences on the following topics: (1) about their experience of using the intervention (2) when and how they used the intervention (3) how easy or not easy they found the intervention to use (4) likes and dislikes about the intervention (5) the functions were most useful and least useful (6) what changes they would make within the intervention.

The data captured will be kept in two different databases based upon whether it is participant-reported or researcher collected. Researcher collected data will be entered into a specially designed password protected online accessed secure database (RedCap). REDCap is run by the Surgical Informatics research group (The University of Edinburgh) under licence from Vanderbilt University. REDCap was developed specifically around HIPAA-Security guidelines. It is hosted within the University of Edinburgh Virtual Machine architecture which is physically secured. Linux web servers running apache2/php5 host the application. Web browser communication to the server is SSL-encrypted by default. All other ports are firewall protected. Data is stored in MySQL databases on a separate server. This server is behind a firewall and can only be accessed from the IP address of the web server. An SSL tunnel encrypts communication between the web and databases servers. File upload is secured between servers using the WebDAV protocol with SSL. "At rest" encryption is in place on the database server. Daily back-ups are made of both servers and stored for four weeks prior to being deleted. Operating security updates are installed automatically. Antivirus software runs to a scheduled protocol on the web server. User passwords are managed directly. Accounts are disabled after 5 failed login attempts. Users are auto logged out after 30 mins of no activity. Users are forced to change password after 42 days. Password strength: AT LEAST 9 CHARACTERS IN LENGTH and must consist of AT LEAST one lower-case letter, one upper-case letter, and one number. Daily audit tracking of users is in place with removal of unused user accounts. Participants who consent using the RedCap e-consent function will enter their

name and signature into the system as part of the consent process. Identifiable electronic information will be kept in a separate database on an NHS server, which will not be accessible outside the immediate research team. These data will be linked by study number to the anonymised research database and will be stored on a secure, password protected location on the local hospital computer drive and only accessible to relevant staff. Researcher collected data will be entered directly into the database using the participant's unique study number.

Patient-reported data will be captured through the HeadOn digital platform (www.headon-health.com) which is hosted on the Microsoft Azure cloud computing service which meets industry standard data protection protocols. As part of the registration process, the patient will input their email address, name and study number into the system. Qualitative interviews will be conducted over the telephone and recorded using a digital voice recorder that generates encrypted audio files. These files will be transcribed by [name] (Edinburgh University MSc student) and kept on the Edinburgh University network. They will be pseudo-anonymised and linked to participant through their research number.

[figure not shown]

Figure 2: Flow chart demonstrating patient reported and researched collected data collected at different time points.

TIMEPOINT**	Enrolment	Allocation	Post-allocation					Close-out
	$-t_1$	0	w_1	w_2	w_3	w_4	w_5	t_x
ENROLMENT:								
Eligibility screen	X							
Informed consent	X							
Allocation		X						
INTERVENTION:								
HeadOn program							↔	
ASSESSMENTS:								
Baseline variables	X	X						
Researcher collected data		X						X
Patient reported data		X	X	X	X	X	X	X
Qualitative interview								X

Table 1: SPIRIT figure for HeadOn feasibility study

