1.2 RATIONALE FOR STUDY

Concussion is common and patients can go on to suffer with a constellation of symptoms which impacts their functional outcome and quality of life (McMahon *et al.*, 2013). Patient provision with information about their concussion and subsequent follow-up was highly variable in a prospective study in the USA (Seabury *et al.*, 2018). This is also the case with psychological therapies despite the fact there is evidence that CBT can help patients manage their symptoms after a concussion (Al Sayegh *et al.*, 2010).

We have developed HeadOn - a web application that delivers a CBT programme to patients following concussion. The application takes the patient through a 5-stage programme including: (i) understanding post-concussion symptoms; (ii) sleep after a concussion; (iii) lifestyle habits and exercise; (iv) managing negative thought patterns and (v) returning to baseline. The programme is delivered through a combination of weekly tasks (such as completing symptom diary, setting exercise goals and setting up a sleep time routine), audio/video media and reading material.

In this study, we would like to examine the feasibility of digitally delivering a course of CBT to patients following concussion. We hypothesise that patients will find it an acceptable and useful form of treatment. We plan on determining recruitment rates to guide future controlled trials.

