2 STUDY OBJECTIVES

2.1 OBJECTIVES

2.1.1 Primary Objective

Our primary objective is to determine the following regarding the digital delivery of CBT to patients following concussion:

- Compliance of participants with a digital CBT program
- Usability of a digital CBT program as a form of therapy

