2.2 ENDPOINTS

2.2.1 Primary Endpoint

1) Participant compliance with CBT program

Data inputted into the digital CBT program will be used as surrogate marker of participant compliance. During each stage of the program participants are required to input data as part of the CBT tasks. Participants will be divided into the following three groups: *Fully compliant*: participants who input data into the program during all five stages; *Partially compliant*: participants who input data but not during all five stages; *Non-compliant*: participants who do not enter any data into the program

2) mHealth App Usability Questionnaire

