7 DATA MANAGEMENT

7.1 Personal Data

Researcher captured anonymised data will be entered into a specially designed password protected online accessed secure database (RedCap). As detailed above, RedCap complies with stringent data security standards and is hosted within the University of Edinburgh Virtual Machine architecture which is physically secured. Participants will be identified on RedCap by study number alone. Patients who consent using the e-consent RedCap function will enter their name and signature into the system as part of the consent process.

Identifiable electronic information will be kept in a separate database, which will not be accessible outside the immediate research team. These data will be linked by study number to the anonymised research database and will be stored on a secure, password protected location on the local hospital (NHS Lothian) computer drive and only accessible to relevant staff.

Identifiable non-electronic data of the participant will be kept in a locked filing cabinet in a locked local research study office. Computers used to collate the data will have limited access measures via usernames and passwords. A fully anonymised version of the data will be shared on the Edinburgh University DataShare service and made available for 5 years after completion of the study.

Published results will not contain any personal data that could allow identification of individual participants.

[figure not shown]

Figure 3: Data flow diagram

Data stream	Data type	Where is database kept?	Who inputs data?	Who has access to data?	Is data anonymous?
HeadOn app www.headon-health.com	Email (mandatory) Name (optional) HeadOn ID Research ID Symptom type/severity Mood Sleep quality Alcohol consumption	Microsoft Azure cloud service	Study participant	Routine clinical care team (EMERGE research nurses) [name] (PI) [name] (MSc student) Pogo Studio Ltd (only if technical issue requiring support)	No. Email and name are identifiable. However, exported data is anonymised with HeadOn / Research ID and file is encrypted
RedCap database	Demographic Clinical examination Imaging findings Outcome data e-consent (name and signature)	Redcap is a medical database platform hosted by Edinburgh University	Routine clinical care team (EMERGE research nurses)	Routine clinical care team (EMERGE research nurses) [name] (PI) [name] (MSc student)	Yes, linked to identifiable patient data through research ID number

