7.2 Transfer of Data

Data entry will be completed by the local research team and data analysis by the study statistician. Participants enter identifiable data (name/email address) outwith the local NHS region as part of the HeadOn registration process and RedCap e-consent function. Participant identifiable data will be removed from any electronic data being sent for analysis.

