8.2 PROPOSED ANALYSES

We plan on conducting the following analyses. The study PI will be performing the analysis:

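### The usability questionnaire, a primary endpoint, is completed through contact with the study's own team, with no private self-completion and no recorded mode, so answers given live could lean towards a favourable rating

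*Combined protocol and SAP*

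**What the plan says.** Section 2.1.1 lists "Usability of a digital CBT program as a form of therapy" as a primary objective beside compliance, and Section 2.2.1 names the matching endpoint: "2) mHealth App Usability Questionnaire".

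Section 6 separates patient-reported from researcher-collected data. At week 5 the Rivermead, PHQ9, sleep and alcohol forms are completed digitally by the participant inside HeadOn. The usability form is handled differently: "The participant will also be contacted by a trained member of the HeadOn research team to complete four questionnaires: the mHealth app usability questionnaire" (followed by healthcare use, return to work and the Glasgow scale). The same contact is used to remind participants about unfinished in-app forms. Section 3 gives the mode: participants are "contacted (via telephone, text or email) by a member of the research team at week 5".

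Section 7.1, Table 2, lists the EMERGE research nurses as the people who enter RedCap data, including outcome data, and as having access to that database. The usability form does not appear in the list of data that participants enter in the app.

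Section 1.2 states: "We have developed HeadOn - a web application that delivers a CBT programme to patients following concussion". It also gives the hypothesis that patients will find the programme acceptable and useful.

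On the analyst, Section 7.2 says "Data entry will be completed by the local research team and data analysis by the study statistician", and Section 8.2 says "The study PI will be performing the analysis".

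**The concern.** The usability form is pure opinion. Its items ask, for example, whether the participant likes the interface and would use the app again. People who give such opinions directly to a member of the study team may soften criticism, most plausibly on a telephone call and less so when they reply by text or email.

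Three features of the plan make this matter:

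- There is no comparator group, so a shift in ratings goes straight into the reported score.
- Any such shift runs in the direction of the stated hypothesis.
- Contact may be by any of three modes, and no section says that the mode is standardised or recorded. Scores from a call and from an email reply would be pooled, and without a record of the mode they could not be reliably separated later.

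The disagreement over the analyst is a separate matter. It affects who makes the analytic choices, not what participants answered.

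**Working it through.** **The plan's own figures.** There are none to reproduce here. The documents give no expected usability score, standard deviation, response rate, share of participants contacted by telephone, or cut-off for an acceptable score. The usability form in the appendix has items scored 1 (strongly agree) to 7 (strongly disagree), so a favourable shift lowers the score. The recruitment target of 100 (Sections 3, 4.1 and 8.1) is the ceiling on respondents.

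**Check 1: mean item score.** All inputs are assumptions: n = 80 respondents, SD = 1.5, and a shift d of 0.25 to 0.75 points among those who answer live. Let q be the share who answer live.

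- Standard error = SD/√n = 1.5/√80 = 0.168.
- Shift in the overall mean = q × d.
- Shift in standard errors = q × d / 0.168.

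| Share answering live (q) | Shift in mean (points) | In standard errors |
|---|---|---|
| 0 | 0 | 0 |
| 0.25 | 0.063 to 0.188 | 0.4 to 1.1 |
| 0.50 | 0.125 to 0.375 | 0.7 to 2.2 |
| 1.00 | 0.25 to 0.75 | 1.5 to 4.5 |

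The last row applies only if every respondent answers live, which the plan does not say. A larger sample does not remove the shift. With n = 100 the standard error is 1.5/√100 = 0.15, and the last row becomes 0.25/0.15 = 1.7 to 0.75/0.15 = 5.0.

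**Check 2: share rating the app favourably.** Again by assumption, let p be the true favourable share and f the fraction of the remaining participants who change their answer because the study team is asking. The observed share is p + f(1 − p).

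- p = 0.50, f = 0 to 0.30: observed 0.50 to 0.50 + 0.30 × 0.50 = 0.65, a rise of 0 to 15 points. The 95% half-width at n = 100 is 1.96 × √(0.5 × 0.5/100) = 0.098.
- p = 0.70, f = 0 to 0.30: observed 0.70 to 0.70 + 0.30 × 0.30 = 0.79, a rise of 0 to 9 points. The half-width is 1.96 × √(0.7 × 0.3/100) = 0.090.

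Both checks give the same reading: the shift could be nothing, and it could match or exceed sampling error. The documents do not say where in that range it lies.

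**Check 3: the analyst.** Sections 7.2 and 8.2, set side by side, assign the analysis to two different roles. No assumption is needed to see the conflict. Table 2 lists no statistician with access to any data stream, so the documents do not confirm that the role is filled.

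**The case against.** The strongest objection concerns who asks. A reader might infer that participants are rating the app to the people who built it. The documents do not support that. Section 6 refers only to a trained member of the HeadOn research team, HeadOn is also the name of the study, and Table 2 has EMERGE nurses entering outcome data. The statement in Section 1.2 that the authors developed the app does not make the person who calls a developer. This part of the objection stands. The concern survives it, because EMERGE staff also approach and recruit participants, and courtesy towards a familiar study team does not require that person to have built the app.

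Second, contact may be by text or email, so the share answering live is unknown and could be small. This also stands, and it is why the point is put as a possibility with a range that starts at zero.

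Third, Section 6 provides voluntary interviews covering dislikes and ease of use, and an online survey for those who decline. Usability therefore does not rest on one score alone. That is fair, but these sources are optional and do not correct the questionnaire score that is the endpoint.

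Fourth, a link may lose people who have stopped using the app, and their absence could also flatter the rating. This is a real cost of self-completion and the reason for keeping a telephone fallback.

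**Conclusion.** The point holds as a possible bias in one primary endpoint that is cheap to reduce. The usability score is gathered through the study's own team, by a mode that is not fixed, with no private completion provided for and no comparator. The size of any shift cannot be derived from the documents. The figures above rest entirely on the assumed shift, SD, number of respondents and share answering live.

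Three stronger readings should be avoided:

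- **That the primary result is biased.** The plan shows only that it could be. Section 8.2 sets no usability cut-off, so there is no defined verdict of usable for the score to be pushed towards.
- **That both primary endpoints are affected.** Compliance is classified from data entered in the app (Sections 2.2.1 and 8.2.3), so this collection route does not touch it.
- **That analysis by the PI distorts the ratings.** It cannot change answers already given. The risk is flexibility in the analysis, which matters because Section 8.2 describes no analysis or scoring of the usability form.

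The contradiction between Sections 7.2 and 8.2 is certain and stands on its own.

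**What to change.** In Sections 3 and 6:

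- Collect the usability questionnaire at week 5 by a self-completed RedCap link sent by text or email. Keep the link outside the app, so that people who have stopped using HeadOn can still answer.
- Extend the week-6 contact explicitly to this form, with telephone as fallback for non-responders. As written, that contact most naturally covers only the in-app questionnaires.
- Record the mode for each participant and report scores by mode. Read differences between modes with care, because those who need a call may differ from those who use the link.
- Do not tell participants that the person contacting them cannot see their answers unless RedCap access rights are set to make that true. Table 2 currently gives the EMERGE nurses access.

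Separately, reconcile Sections 7.2 and 8.2 on the analyst. Preferably the study statistician analyses the primary endpoints from the de-identified export, if that role is filled.

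The cost is one form and one mode field on a platform already used for e-consent, some wording changes, and possibly a change to access rights. Some people will ignore the link, and the telephone fallback addresses this. If no statistician is in post, naming one is an extra cost.
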